3 OBJECTIVES AND ENDPOINTS

OBJECTIVES	ENDPOINTS	JUSTIFICATION FOR ENDPOINTS
Primary		
Compare the effectiveness of usual care to a mobile technology based lifestyle intervention on change in liver and metabolic related parameters.	Reduction in amount of hepatic steatosis (≥5% overall reduction in CAP score) at 6 months.	Hepatic steatosis is a liver specific outcome that has been shown to improve with diet and exercise and is associated with risk of downstream clinical outcome such as development of NASH and cirrhosis.
Secondary		

OBJECTIVES	ENDPOINTS	JUSTIFICATION FOR ENDPOINTS
Improvements in other liver-specific and metabolic outcomes	weight loss, increase in total physical activity (based on step counts)	Weight loss has been associated with histologic improvements in NAFLD and NASH. Physical activity has been shown to improve fibrosis, liver enzymes, metabolic parameters and HRQOL.

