4 STUDY DESIGN

4.1 OVERALL DESIGN

This randomized clinical pilot trial will compare a mobile technology-based lifestyle intervention to a waitlist control group receiving usual care for adult patients with NAFLD. The intervention will use FitBit to track and promote physical activity through tailored longitudinal feedback. Patient will also receive nutritional counseling with serial nutritional assessments. The primary endpoint will be change in amount of hepatic steatosis. Secondary outcomes include changes in weight and physical activity (assessed by trend in step counts). A wait-list control design will be applied. 60 Patients will be randomized to the intervention arm for 6 months and 60 to usual care (the wait-list control). Those initially randomized to the intervention arm will then transition to a 6-month post intervention monitoring period to assess maintenance of behavior change and sustainability of impact on outcomes of interest. Individuals initially randomized to usual care, will transition to the intervention at month 6 for a total of 6 months.

The intervention arm will receive tailored physical activity and nutritional counseling, and the waitlist control arm which will follow usual and customary care for NAFLD patients attending our Heptology clinic for 6 months and then receive the 6-month intervention.

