4.2 SCIENTIFIC RATIONALE FOR STUDY DESIGN

This trial will incorporate a wait-list control that will allow us to maximize our ability to assess the primary outcome (by using a pre-post intervention analysis). The 6-month post-intervention follow-up among those initially randomized to the intervention will allow us to assess maintenance of behavior change.

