6 STUDY INTERVENTION(S) OR EXPERIMENTAL MANIPULATION(S)

6.1 STUDY INTERVENTION(S)

6.1.1 STUDY INTERVENTION OR EXPERIMENTAL MANIPULATION DESCRIPTION

This is a randomized trial comparing a structured mobile technology-based lifestyle intervention compared to usual care.

Intervention

-Education: Patients in the intervention arm will receive our NAFLD educational folder with an overview of contents by study staff. The folder includes: 1) NAFLD disease information including diagnosis, clinical manifestations, natural history and treatments; 2) NAFLD nutritional recommendations including sample menus; 3) NAFLD physical activity recommendations including walking programs and physical activity logs; 4) weight tracking logs; and 5) resources for diet and exercise programs.

-**Physical Activity**: All participants in the intervention arm (N=60) will receive a FitBit Zip for monitoring of step counts. The Fitbit wirelessly syncs data from the tracker to the Fitbit software or app. Study staff will assist with downloading the software and will instruct participants to wear their FitBit during waking hours every day. At any time if the participant has questions or problems regarding the use of the FitBit, a study staff member can be contacted. Study staff will retrieve users' step count data for analysis weekly and will provide subject with personalized feedback on physical activity with tailored step count goals (10% increase per week with max increase 800 steps per week to a maximum of 10,000 steps/week) and motivational messaging via e-mail. Patients with consecutive days without data recorded or with other signs of low FitBit usage (days with minimal step counts) will be contacted by study staff via e-mail or phone if necessary to encourage use. Feedback will occur weekly for the first 3 months of the intervention and then transition to biweekly for the last 3 months. Participants will also complete the short-version IPAQ for physical activity at enrollment, 6 month and 12 month follow-up visits.

-Nutrition: Patients in the intervention arm will have a nutritional assessment by a GI nutritionist specializing in NAFLD either at the enrollment visit if time allows, or in a separate in person or phone assessment within the first 2 weeks of enrollment. All patients will also complete the "Starting the Conversation" nutritional questionnaire for patients with metabolic disease at enrollment, 6 month and 12 month follow-up visits.(15)

Usual Care

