9 STATISTICAL CONSIDERATIONS

9.1 STATISTICAL HYPOTHESES

Primary Efficacy Endpoint:

We hypothesize that participants who complete the lifestyle intervention (as defined by completing the 6 month return visit and data collection) will achieve reduction in amount of hepatic steatosis (\geq 5% reduction in CAP), with those achieving higher percentage weight loss having larger reductions in amount of steatosis.

Secondary Efficacy Endpoints:

We hypothesize that subjects in the intervention arm will be more likely to achieve weight loss and increase their level of physical activity at 6-month compared to usual care.

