9.2 SAMPLE SIZE DETERMINATION

Sample size calculations will be made based on the total N for the cohort. Enrollment of 120 patients in the intervention should provide adequate power to assess for parameters associated with \geq 5% reduction in steatosis and weight loss using 80% power, alpha 0.05. We anticipate a dropout rate of up to 20%.

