9.3.2 ANALYSIS OF THE PRIMARY ENDPOINT(S)

The primary outcome is change in steatosis. This will be assessed by VCTE controlled attenuation parameter (CAP). A \geq 5% *reduction* in CAP score at 6-months and maintenance at 12 months as this has been associated with clinically meaningful improvements in outcomes.

For individuals with missing data (participants who do not complete follow-up imaging), we will analyze as modified intention to treat and a separate analysis among those who completed all data collection elements.

Subjects will be analyzed according to a modified intention to treat analysis. Individuals who were randomized but never provided FitBit data will not be included in the final analysis

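### Section 9.1's definition of completing the intervention fits only the immediate-intervention arm; the pre-post and predictor analyses need pre and post visits set by arm

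*Combined protocol and SAP*

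**What the plan says.** The primary hypothesis in section 9.1 concerns "participants who complete the lifestyle intervention (as defined by completing the 6 month return visit and data collection"). Section 9.3.2 sets the response as a CAP reduction of at least 5%, "in CAP score at 6-months and maintenance at 12 months", and the endpoint table in section 3 also places the primary endpoint at 6 months. None of these gives a separate time origin for the wait-list arm. Section 6.1.1 schedules questionnaires "at enrollment, 6 month and 12 month follow-up visits", so the named visits run from enrollment.

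Section 4.1 randomizes 60 patients to each arm and says of the wait-list: "Individuals initially randomized to usual care, will transition to the intervention at month 6 for a total of 6 months". The heading of Table 2 in section 1.3 likewise puts their intervention after Visit 2.

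Two places rely on data from both arms while on the intervention. Section 4.2 says the wait-list design will "maximize our ability to assess the primary outcome (by using a pre-post intervention analysis"). Section 9.2 says "Enrollment of 120 patients in the intervention should provide adequate power" to find parameters associated with response and weight loss. The synopsis names predictors of steatosis reduction and weight loss as the secondary objective.

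**The concern.** A pre-post analysis needs a value before the intervention and one at its end. In Arm I these are Visits 1 and 2. In Arm II they are Visits 2 and 3. The only completion and response rules in the plan use month 6, which ends the intervention in Arm I and precedes it in Arm II.

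If those rules were applied unchanged to a cohort pooled from both arms, half of the scored periods would contain no intervention. The pooled response rate would mix treatment with usual care, and any association between a patient characteristic and response to the intervention would tend to be diluted. A wait-list patient who stopped shortly after Visit 2 would still meet the 9.1 definition of completion.

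**Working it through.** **The plan's own figure.** The 120 in section 9.2 cannot be reproduced or refuted, because the section gives no response rate, effect size, SD or test. Two things can be checked. From section 4.1, 60 + 60 = 120, so the number in the intervention is reached only by including the wait-list arm. With the stated dropout of up to 20%, 120 × 0.80 = 96, or 60 × 0.80 = 48 per arm if dropout is equal.

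**Timing** (section 1.3, Tables 1 and 2; section 4.1):

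| | Arm I | Arm II |
|---|---|---|
| Intervention period | Day 1 to Day 168 | Day 168 to Day 336 (336 − 168 = 168 days) |
| Visit that ends it | Visit 2 | Visit 3 |
| 6-month visit, counted from enrollment | Day 168 | Day 168 |
| Intervention received by then | full period | none, by the text of 4.1 |
| What the month-12 value shows | 6 months after the intervention | end of the intervention; off study, no later visit |

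**Two readings of section 9.1.**

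1. It covers everyone who receives the intervention. Arm II patients then qualify as completers at Day 168, before starting. The 6-month CAP rule, if carried into the same analysis, measures Day 1 to Day 168, which for them is usual care. Their change from Visit 2 to Visit 3 is not scored.
2. It covers Arm I only. The definition is then correct, but the cohort is 60 (48 after dropout) and not the 120 of section 9.2. The Arm II on-intervention data, which give section 4.2 its reason for the design, have no scoring rule.

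Neither reading is consistent with both 4.2 and 9.2.

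**Extent under the first reading.** 60 of 120 scored periods are usual care, or 48 of 96 after dropout: one half.

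**Size of bias.** Let pT be the response rate over an intervention period, taken as equal in both arms, and pC the rate over a usual-care period. With equal arms, the pooled rate under the written rule is (pT + pC)/2 instead of pT, a shortfall of (pT − pC)/2. All rates are assumptions:

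| pT | pC | Pooled rate as written | Shortfall |
|---|---|---|---|
| 40% | 20% | (40 + 20)/2 = 30% | 10 points |
| 50% | 30% | (50 + 30)/2 = 40% | 10 points |
| 60% | 30% | (60 + 30)/2 = 45% | 15 points |

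Over a wider grid (pT 30% to 60%, pC 10% to 30%, pT above pC) the shortfall runs from 5 to 25 points.

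**Predictors, one assumed case.** Take a binary predictor splitting the 96 into 48 and 48, with response 30% versus 60% on the intervention and 20% in both groups under usual care. The mixed rates are (30 + 20)/2 = 25% and (60 + 20)/2 = 40%. Power of a two-sided 0.05 test of two proportions is 85% with periods set by arm, 35% under the written rule, and 55% using Arm I alone (24 versus 24).

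**The case against.** The other side has real force. The governing words of 9.1 are about completing the intervention, and a patient who has not begun cannot have completed it; the parenthesis may simply mean the visit at the end of a 6-month course. Section 4.2 calls the analysis pre-post with respect to the intervention, and section 8.1 times the 3-month call from the start of the intervention, so the authors do use treatment time. Section 9.3.2 restates the endpoint of section 3, whose objective is the comparison with usual care. Section 9.3 writes out no pooled response rate and no predictor model. Early stoppers are partly covered: 9.3.2 plans a separate analysis of patients with all data collected, and 4.4 requires the last visit for study completion.

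Much of this stands, and it limits the point. A reader might infer that the plan intends to score wait-list patients on usual care. No section says so; it follows only if the written rules are carried over unchanged. A reader might also infer that month 6 is the wrong time for the CAP endpoint. It is the right time in both arms for the randomized comparison. Sections 4.1 and 4.2 already attach maintenance to the arm first randomized to the intervention.

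What does not stand is that the text resolves itself. Where treatment time was meant for the telephone call, section 8.1 says so; section 9.1 does not. If the 6 and 12 months of 9.3.2 were treatment time in both arms, Arm II would need a visit at month 18 (6 + 12), and it leaves the study at Visit 3. Section 9.3.7 lists data by time point for a pre-post comparison without saying which points are pre and post in each arm, so the choice could be made after the data are seen.

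**Conclusion.** The point holds as a fault in a stated definition. Completion in 9.1 is either wrong for Arm II or limited to Arm I and at odds with the 120 in 9.2. It concerns the pre-post, completer and predictor analyses and leaves the randomized contrast at month 6 untouched. It should be corrected before analysis.

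Up to half of the scored periods are affected: 60 of 120, or 48 of 96 with 20% dropout shared equally. The bias cannot be fixed from the documents, which give no response rates. The shortfall of 10 to 15 points rests on the assumed pairs 40%/20% to 60%/30%, on equal arms, and on the same on-intervention response in both. The power figures are one assumed example.

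Nothing here shows that 120 is too few or too many; section 9.2 lacks the inputs to test it.

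**What to change.** - **Section 9.1:** define completion as attending, with data collection, the visit that ends the 6-month intervention period: Visit 2 in Arm I, Visit 3 in Arm II.
- **Pre-post, completer and predictor analyses:** state pre and post by arm. Arm I: Visit 1 to Visit 2. Arm II: Visit 2 to Visit 3. Apply this to both CAP and weight.
- **Randomized comparison with usual care:** keep Day 1 to Visit 2 in both arms.
- **Section 9.3.2:** say that maintenance at 12 months applies to Arm I, in line with 4.1 and 4.2.
- **Table 2, section 1.3:** it marks FitBit provision and the dietician assessment at Visit 1 for the wait-list arm, while 4.1 and the table's own heading start the intervention at month 6, after Visit 2. These must be reconciled, because Visit 2 serves as a clean pre-intervention value only if nothing in the intervention came before it.

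The analysis changes are wording only: CAP (through VCTE) and weight are already scheduled at Visits 1, 2 and 3 in both arms. Reconciling Table 2 needs a check of what is actually provided at Visit 1.

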9.2 SAMPLE SIZE DETERMINATION

Sample size calculations will be made based on the total N for the cohort. Enrollment of 120 patients in the intervention should provide adequate power to assess for parameters associated with \geq 5% reduction in steatosis and weight loss using 80% power, alpha 0.05. We anticipate a dropout rate of up to 20%.

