1 PROTOCOL SUMMARY

1.1 SYNOPSIS

Title:	A Randomized Controlled Pilot trial of a Structured Mobile Technology Based Lifestyle Program Vs Usual Care for Patients with Non-Alcoholic
	Fatty Liver Disease
Grant Number:	AWD007197
Study Description:	Lifestyle interventions remain first line therapy for the treatment of
Study Description.	non-alcoholic fatty liver disease (NAFLD). In clinical practice, it is challenging for patients to initiate and maintain these changes. In this randomized clinical pilot trial, we will evaluate impact of a structured mobile technology-based lifestyle intervention program compared to usual care to among patients with NAFLD. We hypothesize individuals randomized to the intervention arm will have significantly improved
	outcomes compared to usual care, and that the intervention will be
	feasible, low cost and amenable to large scale implementation.
Objectives:	Primary objective: compare the effectiveness of usual care to a mobile technology based lifestyle intervention on change in liver and metabolic related parameters.
	Secondary objectives: identify predictors associated with reduction in hepatic steatosis and weight loss.
Endpoints:	Primary Endpoint: change in amount of hepatic steatosis
	Secondary Endpoints: change in weight, change in physical activity
Study Population:	120 adult patients with NAFLD including steatosis only, non-alcoholic steatohepatitis (NASH) and NAFLD-related compensated cirrhosis seen in the Michigan Medicine Hepatology clinic.
Phase or Stage:	N/A
Description of Sites/Facilities Enrolling	
Participants:	Michigan Medicine Hepatology Clinics, and patient identified through
i il cicipantor	Data Direct and EMERSE in various local clinics
Description of Study	
Intervention/Experimental	Personalized adaptive lifestyle intervention program that includes
Manipulation:	physical activity and nutritional feedback compared to usual care
Study Duration:	18 months
Participant Duration:	13 months

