1.2 SCHEMA

[figure not shown]

Figure 1. All participants will be enrolled in the study for ~12 months and will complete 3 study visits. Individuals randomized to the Intervention arm will have 6 months of intervention followed by 6 months of follow-up to assess for behavior change maintenance. Individuals randomized to the Usual Care Waitlist will be followed for 6 months, after which they will start a 6-month intervention period.

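### The only power statement (section 9.2) concerns 120 treated patients and predictors of response; the primary comparison of 60 with 60 has none, and sections 4.2, 9.1 and 9.3.2 do not carry the usual-care comparator into the primary analysis

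*Combined protocol and SAP*

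**What the plan says.** **Objective and design.** The synopsis (1.1) gives "Primary objective: compare the effectiveness of usual care to a mobile technology based lifestyle intervention on change in liver and metabolic related parameters". Section 3 repeats this and sets the endpoint as a CAP reduction of at least 5%: "overall reduction in CAP score) at 6 months". Section 4.1 gives the allocation: "60 Patients will be randomized to the intervention arm for 6 months and 60 to usual care (the wait-list control"). The wait-list arm is treated later (1.2): "Individuals randomized to the Usual Care Waitlist will be followed for 6 months, after which they will start a 6-month intervention period".

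**Sample size.** Section 9.2 says that the calculation rests on the total cohort. It then claims 80% power at alpha 0.05: "Enrollment of 120 patients in the intervention should provide adequate power to assess for parameters associated with" CAP reduction and weight loss. Dropout is expected to be up to 20%. The synopsis lists the matching aim as secondary: "Secondary objectives: identify predictors associated with reduction in hepatic steatosis and weight loss".

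**Primary analysis.** Section 4.2 says that the wait-list design will "maximize our ability to assess the primary outcome (by using a pre-post intervention analysis"). The primary hypothesis in 9.1 concerns "participants who complete the lifestyle intervention (as defined by completing the 6 month return visit and data collection") and adds that greater weight loss will go with larger reductions in steatosis. The secondary hypothesis in the same section is stated against usual care. Section 9.3.2 specifies a modified intention-to-treat analysis and a separate analysis of those with complete data. It leaves out randomised people who never supplied FitBit data, and it names no between-arm test or contrast.

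**The concern.** The power claim and the primary question differ in three respects: the number of patients, the group they form and the analysis applied to them. A reader who meets 80% power and 120 in section 9.2 will naturally attach both to the randomised comparison, which has 60 per arm.

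The second issue is what will be estimated. Someone working from section 3 would compare the arms at 6 months. Someone working from 4.2 and the primary hypothesis in 9.1 could analyse change from baseline in treated patients, and 9.3.2 does not settle which is primary. A pre-post analysis counts as intervention effect any change that would also have occurred under usual care, which section 6.1.1 describes as including brief lifestyle advice. It would not answer the stated primary objective.

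**Working it through.** **1. Can the plan's own figure be reproduced?** No. Section 9.2 gives no response rate, mean CAP change, SD, predictor prevalence, association size or test. Only the dropout arithmetic can be checked:

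- 120 × 0.80 = 96 in total, and 60 × 0.80 = 48 per arm.
- In reverse, 96 / 0.80 = 120, so 120 may already allow for dropout. Section 9.2 does not say.

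**2. Where do 120 treated patients come from?** By month 6, 60 have been assigned to the intervention (4.1). Adding the 60 wait-list patients treated from month 6 to month 12 (1.2, 4.1) gives 60 + 60 = 120. The figure is therefore attainable for a pooled analysis of treated patients, but not for the 6-month comparison.

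**3. Which sections carry the comparator for the primary outcome?**

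| Section | Primary outcome framed as | Usual care named? |
|---|---|---|
| 1.1, 3 (objective) | Intervention compared with usual care | Yes |
| 4.1 | 60 versus 60, wait-list control | Yes |
| 4.2 | Pre-post analysis | No |
| 9.1, primary | Reduction among intervention completers | No |
| 9.1, secondary | Weight and activity against usual care | Yes |
| 9.2 | Parameters associated with response, 120 treated | No |
| 9.3.2 | Modified ITT, plus a separate completer analysis | No |

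**4. What can 60 versus 60 detect?** Inputs from the plan: 80% power and alpha 0.05 (9.2), two-tailed tests (9.3.1), and 60 per arm (4.1) or 48 after 20% dropout. The usual-care response rate p0 is my assumption. With p̄ = (p0 + p1)/2, solve for p1:

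(p1 − p0)√n = 1.96 √[2p̄(1 − p̄)] + 0.842 √[p0(1 − p0) + p1(1 − p1)]

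For example, p0 = 0.20, n = 60 and p1 = 0.436 give 1.828 on the left and 1.291 + 0.536 = 1.827 on the right.

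| Assumed usual-care rate | Detectable rate, 60/arm | Difference | Detectable rate, 48/arm | Difference |
|---|---|---|---|---|
| 10% | 30% | 20 points | 33% | 23 points |
| 20% | 43.6% | 24 points | 46.6% | 27 points |
| 30% | 55.0% | 25 points | 58.0% | 28 points |
| 40% | 65.3% | 25 points | 68.2% | 28 points |

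For the 20%, 30% and 40% rows, full binomial enumeration of the uncorrected chi-square test gives power of 0.80 to 0.81.

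**5. Precision of the difference.** The 95% CI half-width is 1.96 √[p1(1 − p1)/n + p2(1 − p2)/n]:

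| Assumed rates | 60/arm | 48/arm |
|---|---|---|
| 20% and 20% | 14 points | 16 points |
| 30% and 55% | 17 points | 19 points |
| 50% and 50% | 18 points | 20 points |

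**6. CAP change as a continuous outcome.** A two-sample t-test (noncentral t) with 80% power detects 0.516 SD at 60 per arm and 0.578 SD at 48 per arm.

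**The case against.** Several points on the other side have force.

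- *The protocol does name usual care.* It does, in the synopsis, section 3 and section 4.1. This is therefore a conflict between sections and not a missing comparator.
- *Section 9.2 discloses its basis.* Its opening sentence refers to the total cohort, and 4.1 explains how all 120 come to be treated. The pooled basis is hinted at but not spelled out. Nor is the predictor aim purely secondary, because the weight-loss clause in 9.1 places part of it in the primary hypothesis.
- *This is a pilot.* A precision argument would be acceptable, and the summary of changes justifies 120 by margin of error. But 9.2 asserts 80% power and gives no precision figure.

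A reader might also infer more than the documents support:

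- *That the primary analysis is an uncontrolled analysis of completers.* This joins the pre-post wording of 4.2 to the completer wording of 9.1. Section 9.3.2 makes modified ITT the main analysis and completers a separate one. The missing element is the between-arm contrast.
- *That the protocol itself predicts improvement under usual care.* The remark in 2.2 about placebo effects concerns drug trials, and the same section says that uptake of lifestyle change is very limited in practice. The argument for a comparator is general and does not need that attribution.
- *That 48 per arm is a floor.* Dropout is given as up to 20% with no time point, 7.2 allows some replacement, and the FitBit-data exclusion in 9.3.2 could reduce either arm further.
- *That 9.3.7 prescribes a pre-post primary analysis.* It describes a listing of individual data only.

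**Conclusion.** The inconsistency is real and should be corrected before analysis. The one power claim concerns pooled treated patients and predictors of response. The primary randomised comparison has no stated power, precision or detectable effect, and 4.2, 9.1 and 9.3.2 leave open whether the primary analysis uses the control arm at all.

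It is tempting to conclude that the trial is underpowered or that 120 is an arithmetic mistake. Neither follows. The plan states no expected between-arm effect against which to judge power, and 120 is a correct count of patients eventually treated if none are lost.

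The detectable differences of about 20 to 28 points (usual-care rates of 10% to 40%, 48 to 60 per arm), the half-widths of about 14 to 20 points for the rate pairs examined, and the 0.52 to 0.58 SD describe the sensitivity of the design. The response rates behind the first two are assumptions, since the documents give none. The text findings do not depend on them.

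**What to change.** 1. **4.2, 9.1 and 9.3.2:** state that the primary analysis of CAP response at 6 months compares the randomised intervention and usual-care arms. Label pooled pre-post analyses supportive. Keep the completer analysis as the separate analysis that 9.3.2 already names.
2. **9.3.2:** reconcile this with the exclusion of randomised people who never supplied FitBit data. Section 6.1.1 describes the FitBit for the intervention arm, while Table 2 marks its provision to the wait-list arm at both visits 1 and 2. Apply no post-randomisation exclusion that works differently by arm.
3. **9.2:** state 120 randomised 1:1, 60 per arm, and about 48 per arm at 20% dropout before any other exclusion. Say whether 120 already allows for dropout. Attach the pooled number of about 96 to 120 to the predictor analysis only.
4. **9.2:** do not attach the 80% claim to the primary comparison as it stands. Give its detectable difference or CI half-width from the ranges above, with the assumed rates labelled as such.

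Section 9.3.7 needs no change. The cost is a rewritten paragraph in 9.2 and short edits in three other sections. No patients, visits or tests are added, because VCTE at visit 2 (day 168) is already scheduled in both arms. The price is a less favourable stated detectable effect for the primary comparison.
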